8.4 Study Treatments

8.4.1 Extent of Exposure

The duration of treatment (in days), the duration of treatment period (in days), the duration of study (in days), the total dose administered (in mg), the number of injections per subject, the number of missed injections per subject, the number of missed injections per subject due to COVID-19, the proportion of subjects who missed at least one injection, the proportion of subjects who missed at least one injection due to COVID-19 will be summarized by treatment group for the Safety Set.

The duration of treatment (in days) is defined as the number of days from the date of first treatment injection through the date of the last treatment injection, inclusive, adding 1 day (i.e. date of last treatment injection – date of first treatment injection + 1).

The duration of treatment period (in days) is defined as the number of days from the date of first treatment injection through the date of the end of treatment period as collected in the CRF, inclusive, adding 1 day (i.e. date of end of treatment period – date of first treatment injection + 1).

The duration of study (in days) is defined as the number of days from the date of signature of first informed consent (across all screening occurrences) through the date of the end of participation (across all screening occurrences), inclusive, adding 1 day (i.e. date of end of participation – date of signature of first informed consent + 1).

8.4.2 Treatment Compliance and Modifications

Dosage modifications of the study drug will not be permitted during the clinical study. Any inadvertent dose modifications should be reported to the sponsor/Contract Research Organization (CRO).

Treatment compliance will be assessed through the treatment record and drug dispensation logs. Dosing frequency is scheduled for every 4 weeks, based on the baseline/Day 1 visit date. If a study visit occurs outside the visit window, study drug can be administered provided there is a minimum of three weeks since the last injection. Future visits should be scheduled within the required windows based on the baseline/Day 1 visit date, while maintaining the minimum 3-week interval between two injections.

The overall compliance in percent will be calculated as the ratio of the total number of actual injections during the treatment period divided by the total number of expected injections during the treatment period multiplied by 100.

Dose compliance will be documented in the CRF, with the total volume (mL) of the study drug that was properly administered. Total volume injected in mL is converted into total dose administered in mg following the correspondence below:

Volume injected (mL)	Dose administered (mg)
0.49 mL	30 mg dual-chamber, single-use syringe (DCS)

Injected volume is assumed to be proportional to the dose administered.

Subjects are considered as compliant when their compliance is $\geq 80\%$ and $\leq 120\%$.

The overall compliance until Week 8, the compliance by visit and the number of injections received and missed per subject will be presented in a table by treatment for the Safety Set. The number of missing injections will be based on the full treatment period (six injections) and will not be adjusted for subjects that terminate treatment early (i.e. a subject that received 2 injections at baseline and then discontinued before Week 4 will be counted as missing 4 injections). A corresponding listing will be provided for exposure and compliance. Details of study drug administration at each visit will also be listed.

9 Efficacy Analysis

Efficacy assessments will be conducted for all subjects at the screening visit (upon signing of the ICF) and at every subsequent visit as described in schedule of assessments in [Appendix A](#). All efficacy assessments will be listed in by-subject listing.

All efficacy analyses will be performed in the ITT Set. The primary efficacy analysis will be repeated in the mITT Set and PP Set as supportive evidence and to assess robustness of efficacy findings.

Subjects will be summarized and analyzed according to their randomized treatment group.

Summaries based on observed case (OC) will be provided for all primary, secondary, and exploratory efficacy endpoints without imputation of any missing data. For the OC summaries, if any rescue therapy is received or treatment is discontinued, and data are collected post-rescue receipt or treatment discontinuation, then the data post-rescue or post-discontinuation will be summarized as observed.

Proportion of subjects with WI NRS/SD NRS ≥ 4 and WI NRS ≥ 3 , changes and percent changes from baseline of WI NRS/SD NRS at each week (from week 1 through week 20) will be calculated on the basis of the weekly average, obtained by averaging at least 4 daily WI NRS/SD NRS scores over 7-day periods.

For baseline weekly average, if fewer than 4 daily WI NRS/SD NRS scores for the 7-day period are available, the interval lower bound will be extended up to 7 additional days, one day at a time, until 4 daily WI NRS/SD NRS scores are available. If after the interval extension fewer than 4 daily WI NRS/SD NRS scores are available, the baseline weekly average WI NRS/SD NRS will be considered missing.

For week 12 weekly average, if fewer than 4 daily WI NRS/SD NRS scores for the 7-day period are available, the interval upper bound will be extended for 5 additional days, one day at a time, until 4 daily WI NRS/SD NRS scores are available. If after extending the upper bound fewer than 4 daily WI NRS/SD NRS scores available, the interval lower bound will be extended for 5 additional days, one day at a time, until 4 daily scores are available. If after the interval extension fewer than 4 daily WI NRS/SD NRS scores are available, the week 12 weekly average WI NRS/SD NRS will be considered missing.

For all the other weekly averages, if fewer than 4 daily WI NRS/SD NRS scores for the 7-day period are available, the weekly average WI NRS/SD NRS will be considered missing for that period.

For the aim of sensitivity analyses, weekly averages of WI NRS obtained by averaging at least 3 daily scores over 7-day periods, at least 2 daily scores over 7-day periods and at least 1 daily score over 7-day periods will be calculated. No period extension at baseline and week 12 applies for these weekly averages. If fewer than 3, 2 or 1 daily WI NRS scores for the 7-day period are available, the corresponding weekly average of WI NRS will be considered missing for that period.

Data of both nemolizumab groups (30 mg and 60 mg) and placebo group and comparisons versus placebo group of both nemolizumab groups will be presented.

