12 TREATMENTS

12.1 Details of Study Medication

12.1.1 Investigational Products Administered

“Study drug” or “study medication” refers to nemolizumab or placebo drug product for purposes of this double-blind study. The list of excipients is detailed in the IB.

The Sponsor has developed a lyophilized powder in a DCS which holds the lyophilized nemolizumab or placebo, and the sterile water for injection separately.

Subjects will receive a loading dose of nemolizumab (60 mg) or placebo by two SC injections at baseline (30 mg + 30 mg, placebo + placebo), and a 30 mg or 60 mg dose of nemolizumab or placebo by two SC injections (30 mg + placebo, 30 mg + 30 mg, placebo + placebo) at Weeks 4 and 8. All the study drug treatment should be performed within four hours following the completion of the hemodialysis .

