3.1 Overall Study Design and Plan

This is a randomized, double-blind, placebo-controlled, multicenter, parallel-group study to evaluate the efficacy and safety of nemolizumab in adult subjects with moderate to severe CKD-aP.

Subjects will be randomized in one of the following three arms/groups (two different doses of nemolizumab and a placebo) in a 1:1:1 ratio:

[figure not shown]
- Group 1: 30 mg Nemolizumab Q4W with a 60 mg loading dose at baseline;
- Group 2: 60 mg Nemolizumab Q4W without loading dose at baseline;
- Group 3: Placebo Q4W.

Approximately 84 subjects will be randomized in each nemolizumab group and in the placebo group for a total sample size of approximately 252 subjects.

In order to maintain the blind, all subjects will receive 2 injections at each administration (30 mg + 30 mg or 30 mg + placebo or placebo + placebo).

The study consists of a screening period (up to 4 weeks), a 12-week treatment period, and an 8-week follow up period (12 weeks after the last study drug injection). The screening period will evaluate subject eligibility. At the baseline visit, subjects will receive an initial dose of nemolizumab 60 mg or placebo by two subcutaneous (SC) injections (30 mg + 30 mg, or placebo + placebo). Study drug treatment with either nemolizumab or placebo should start after completion of the hemodialysis treatment (within four hours). Then study drug (i.e., nemolizumab 30 mg, nemolizumab 60 mg or placebo) will be administered via two SC injections (30 mg + placebo, 30 mg + 30 mg, or placebo + placebo) at Week 4 and Week 8 after completion of hemodialysis treatment (within four hours). **CCI** [REDACTED] are to be taken before hemodialysis. [Figure 1](#) below presents the study design:

Figure 1

R = Randomization; * = Visits with study drug administration

Note: All subjects in each arm will receive 2 injections at each administration (either 30 mg + 30 mg, or 30 mg + placebo, or placebo + placebo) in order to maintain the blind

The schedule of assessments is summarized in [Appendix A](#).

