3.3 Treatments

This study has three treatment arms at a ratio of 1:1:1. Subjects will receive a loading dose of nemolizumab (60 mg) or Placebo by two SC injections at baseline (30 mg + 30 mg, placebo + placebo) and a 30 mg or 60 mg dose of nemolizumab or placebo by two SC injections (30 mg + placebo, 30 mg + 30 mg, placebo + placebo) at Week 4 and at Week 8. All the study drug treatment should be performed following the completion of the hemodialysis treatment (within four hours). Table 1 below summarizes the study drug dosing during the treatment period of the study.

Table 1 Treatment Period Dosing by Treatment Group

Group	Treatment	Dose at Day 1/Baseline	Dose at Week 4 and Week 8	Route	Schedule
1	30 mg Nemolizumab (CD14152)	60 mg (two 30 mg injections)	30 mg (30 mg injection + placebo injection)	SC	Q4W
2	60 mg Nemolizumab (CD14152)	60 mg (two 30 mg injections)	60 mg (two 30 mg injections)	SC	Q4W
3	Placebo	Placebo (two placebo injections)	Placebo (two placebo injections)	SC	Q4W

Abbreviation(s): Q4W = every four weeks; SC = subcutaneous.

4 General Statistical Considerations

All summaries and results in Tables, Listings and Figures (TLFs) should be presented for the following groups:

Table 2 Treatment Group Labels in TLFs

Treatment Groups	Label in TLFs
60 mg loading dose of nemolizumab by two SC injections of 30 mg at Baseline, followed by one SC injection of 30 mg of nemolizumab + one SC injection of placebo at Week 4 and at Week 8	Nemolizumab 30 mg
Two SC injections of 30 mg of Nemolizumab at Baseline, at Week 4 and at Week 8	Nemolizumab 60 mg
Two SC injections of placebo at Baseline, at Week 4 and at Week 8	Placebo
Nemolizumab 30 mg, Nemolizumab 60 mg, and Placebo treatment groups combined	Total

The reference date for the calculation of study days will be the date of the first treatment injection on Day 1/Baseline for subjects randomized and treated or the date of randomization for subjects randomized but not treated (if any).

For events/assessments on or after the reference date, the study day of events/assessments is calculated as the date of event minus the reference date + 1. For events/assessments before the reference date, the study day of the events/assessments is calculated as the date of assessment minus the reference date.

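### The volume-to-mg conversion in SAP 8.4.2 does not exclude placebo syringes, so a full course converts to 180 mg in every arm, placebo included

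*SAP*

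**What the plan says.** SAP 8.4.1 lists the exposure variables to be summarised by treatment group in the Safety Set. They include "the total dose administered (in mg), the number of injections per subject".

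SAP 8.4.2 says how the mg figure is obtained. The CRF documents dose compliance "with the total volume (mL) of the study drug that was properly administered". Then: "Total volume injected in mL is converted into total dose administered in mg following the correspondence below". The correspondence has one row, 0.49 mL against a 30 mg dual-chamber syringe, followed by the statement "Injected volume is assumed to be proportional to the dose administered".

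Three other passages fix what enters that volume:

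- Protocol 12.1.1 says that study drug "refers to nemolizumab or placebo drug product".
- SAP 3.1 says that "all subjects will receive 2 injections at each administration", to keep the blind. The SAP 8.4.2 count of missed injections uses six for the full treatment period.
- SAP 3.3, Table 1, gives the content. In the 30 mg arm both baseline syringes are active, and one of the two is placebo at Weeks 4 and 8. In the 60 mg arm all six are active. In the placebo arm all six are placebo.

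**The concern.** The design keeps the blind by giving every subject the same number of injections, so injected volume carries no information about which arm a subject is in. A rule that turns total injected volume into mg at the active syringe's strength therefore credits placebo syringes with drug.

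At stake is the correctness of one reported quantity: total dose administered in mg, in Table 14.1.4.1 and Listing 16.2.5.2 (Extent of Exposure and Compliance). Protocol 19.4.1 asks only for duration of exposure and number of administrations. The mg variable is thus defined in the SAP alone, and there is no second definition to fall back on. A programmer who follows SAP 8.4.2 to the letter would report the same full-course dose in all three arms.

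**Working it through.** **Inputs**

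- Conversion: 0.49 mL = 30 mg, proportional (SAP 8.4.2).
- Active syringe: 61.5 mg/mL after reconstitution, 0.49 mL injected (Protocol 8.5).
- Injections per full course: 2 per visit x 3 visits = 6 in every arm (SAP 3.1, 3.3 and 8.4.2).
- Active and placebo syringes per arm: 4 + 2 (30 mg arm), 6 + 0 (60 mg arm), 0 + 6 (placebo), from SAP Table 1.
- Placebo syringe volume: no number is given. Protocol 8.5 says that placebo is reconstituted and administered as the active product is, so 0.49 mL is assumed.

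**Step 1: the plan's own factor.** 61.5 mg/mL x 0.49 mL = 30.1 mg. The 30 mg per 0.49 mL is right for an active syringe.

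**Step 2: the rule as written, full course.** Volume = 6 x 0.49 = 2.94 mL in every arm. Dose = 2.94 / 0.49 x 30 = 180 mg in every arm.

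**Step 3: scheduled nemolizumab from Table 1.** 30 mg arm: 60 + 30 + 30 = 120 mg. 60 mg arm: 60 + 60 + 60 = 180 mg. Placebo: 0 mg.

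**Step 4: comparison.**

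| Arm | Rule as written | Scheduled | Excess |
|---|---|---|---|
| 30 mg | 180 mg | 120 mg | 60 mg (60/120 = 50%) |
| 60 mg | 180 mg | 180 mg | 0 |
| Placebo | 180 mg | 0 mg | 180 mg |

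**Step 5: how far the assumed placebo volume matters.** For a placebo syringe of v mL, the excess is 2v / 0.49 x 30 mg in the 30 mg arm and 6v / 0.49 x 30 mg on placebo. At v = 0.49 these are 60 and 180 mg. They vanish only at v = 0, so the direction of the error does not rest on the exact volume.

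**Step 6: the same rule restricted to active syringes.** 30 mg arm: 4 x 0.49 = 1.96 mL, giving 120 mg. 60 mg arm: 2.94 mL, giving 180 mg. Placebo: 0 mL, giving 0 mg. All three now match Table 1.

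**The case against.** The best defence is that the rule was meant for active syringes only. The dose cell names a 30 mg dual-chamber syringe. Elsewhere the documents use 30 mg for the active syringe and placebo for the other, and Protocol Table 2 gives the placebo dosage as not applicable. On that reading a placebo syringe has no mg equivalent. SAP 17 also leaves programming detail to the table shells, which are not in the public documents, and a placebo column showing 180 mg would probably be caught at output review.

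The active-only reading is possible and may well be what was intended. But the operative sentence refers to total volume injected, the proportionality statement carries no restriction, and no visible passage excludes placebo volume or says how active syringes would be identified. It is better to settle this in the text than to rely on someone noticing.

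It is also fair to object that little depends on the variable, and that objection stands. Three stronger inferences are tempting, and the documents do not support them:

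- **That compliance has the same fault.** It does not. Compliance is actual over expected injections and uses no mg conversion. A 30 mg arm subject who missed the only active syringe at Week 4 but received the placebo one would score 5/6 = 83.3%, above the 80% limit, with 90/120 = 75% of scheduled active drug. Nothing suggests that this pattern is expected. The SAP also reports compliance by visit and missed injections, and the 80% limit defines no analysis set. The PP Set requires all scheduled doses.
- **That safety rates would be distorted.** SAP 4 takes the number of subjects in the treatment group as the denominator, and SAP 12 summarises adverse events by actual treatment group. No analysis per mg is visible.
- **That dose selection would be misled.** SAP 15 bases it on risk-benefit at the final analysis. Part of that section is redacted, and nothing visible uses total mg. The arms remain distinguished by their labels and dosing schedules (SAP Table 2).

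**Conclusion.** The point holds as a defect in one descriptive exposure variable. Read literally, SAP 8.4.2 gives a wrong total dose in two of the three arms: 60 mg (50%) too high in the 30 mg arm and 180 mg too high on placebo. It is correct only in the 60 mg arm.

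The figures assume a 0.49 mL placebo syringe and a subject who receives all six injections. With missed or partial injections the converted total falls with the volume given, but placebo volume is still counted as drug. The conclusion also assumes that no unseen shell or specification already restricts the conversion to active syringes.

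The effect is limited to the exposure table and listing. It deserves correction before database lock because the written rule and the dosing table cannot both be followed, and the remedy is short.

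**What to change.** In SAP 8.4.2, state that the conversion of 0.49 mL to 30 mg applies only to nemolizumab syringes, identified after unblinding from the IRT syringe assignment, and that placebo syringes contribute 0 mg. Define total dose administered in SAP 8.4.1 as total nemolizumab dose on that basis.

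Add one sentence on the level at which volume is recorded. The SAP speaks of a total volume and does not say whether it is held per syringe. If it is only a visit total, derive mg from the number of active syringes given and state how a partial injection is handled at visits where one syringe was active and one placebo.

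Leave injection-count compliance as planned.

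The cost is a few lines of SAP text and one programming step. Protocol 12.2.2 has the IRT assign each syringe, so syringe identity should need no new collection. Because the link is made after unblinding, the blind is not touched. Per-syringe volume is the one item whose availability the documents do not confirm, which is why the count-based fallback should be written in.

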9.1 Analysis of Primary Efficacy Endpoint

An overview of the analyses for primary efficacy is given in [Appendix B](#).

9.1.1 Primary Analysis of the Primary Efficacy Endpoint (Estimand 1)

A summary will be provided for the primary efficacy endpoint without any imputation of missing data. Note that subjects who took rescue therapies at any point up to and including Week 12 are considered as treatment failures in this endpoint.

In the main statistical analysis described below, missing WI NRS weekly average values will be imputed for the ITT set using multiple imputations (MI) under missing at random (MAR) assumption. Worst values are assumed after use of rescue therapy or treatment discontinuation due to lack of efficacy or AE/death related to study drug prior to imputation. Dichotomous endpoints will be calculated from the underlying imputed variable. See [Appendix C](#) for details about Multiple Imputation.

The proportion of subjects with an improvement at Week 12 of WI NRS ≥ 4 from baseline without use of rescue therapies and without treatment discontinuation due to lack of efficacy or AE/death related to study drug will be analyzed in the ITT Set for each multiply imputed dataset, using the Cochran-Mantel-Haenszel (CMH) test stratified by analysis center; strata-adjusted difference in proportions between treatment groups (Nemolizumab – Placebo) and the 97.5% confidence interval (CI) of the difference will be based on the large sample approximation method for binary data using Mantel-Haenszel strata weights⁸ and the Sato variance estimator⁹. This analysis will be performed for both dosing schedules compared to placebo using the “Commonriskdiff” and “CL=MH” options in SAS PROC FREQ. Proportions and strata-adjusted difference in proportions will be pooled using Rubin’s method. Results from the CMH analysis will be combined using the Wilson-Hilferty transformation as described in the Bohdana Ratitch, et al. paper¹⁰ to produce a pooled CMH test p-value.

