4.4 Multiplicity Adjustment for Primary and Key Secondary Efficacy Endpoints

In order to maintain the overall two-sided alpha of 0.05, a two-sided alpha of 0.025 will be spent for the comparison of each nemolizumab dose group versus placebo group. A predefined hierachal testing procedure will be implemented to test the primary and key secondary endpoints of each nemolizumab dose group versus placebo group.

The following hypothesis test will be evaluated for the primary endpoint at the two-sided alpha of 0.025:

$$\begin{cases} H_0: \pi_{Nemolizumab} = \pi_{Placebo} \\ H_a: \pi_{Nemolizumab} \neq \pi_{Placebo} \end{cases}$$

where $\pi_{Nemolizumab}$ is the proportion of subjects in nemolizumab group with an improvement of WI NRS ≥ 4 from baseline at Week 12 and $\pi_{Placebo}$ is the proportion of subjects in placebo group with an improvement of WI NRS ≥ 4 from baseline at Week 12.

The hypothesis tests for the key secondary efficacy endpoints are conditional on the success of the primary endpoint. The hypothesis tests for the key secondary efficacy endpoints will be evaluated on the ITT Set according to the following predefined order, all at the same two-sided alpha of 0.025, moving to the next hypothesis test only after a success on the previous hypothesis test. This approach does not inflate the type I error rate as long as the hypothesis tests for the key secondary efficacy endpoints are conditional on the success of the primary, there is a prospective specification of the testing sequence and no further testing is performed once the sequence breaks, that is, further testing stops as soon as there is a failure of a hypothesis test in the sequence to show significance at the predefined alpha level.

Key Secondary Efficacy Endpoints:

1. Proportion of subjects with an improvement of WI NRS ≥ 3 from baseline at Week 12.
2. Proportion of subjects with an improvement of WI NRS ≥ 4 from baseline at Week 4.
3. Proportion of subjects with an improvement of SD NRS ≥ 4 from baseline at Week 12.
4. Proportion of subjects with an improvement of WI NRS ≥ 3 from baseline at Week 4.
5. Proportion of subjects with an improvement of SD NRS ≥ 4 from baseline at Week 4.

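### SAP 9.1.1: pooling 1-df CMH statistics by Wilson-Hilferty is slightly anti-conservative at alpha 0.025; pooling the signed CMH statistic by Rubin's rules corrects it

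*SAP*

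**What the plan says.** SAP 4.4 fixes the error rate. It says "In order to maintain the overall two-sided alpha of 0.05, a two-sided alpha of 0.025 will be spent for the comparison" of each dose with placebo, and then "The following hypothesis test will be evaluated for the primary endpoint at the two-sided alpha of 0.025". A failure at the primary endpoint stops the key secondary tests for that dose.

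SAP 9.1.1 fixes the test. Each imputed data set is analysed "using the Cochran-Mantel-Haenszel (CMH) test stratified by analysis center", and "This analysis will be performed for both dosing schedules compared to placebo". The response is binary and each comparison has two arms, so each CMH statistic has 1 degree of freedom.

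The estimate and the p-value then take different routes. For the estimate, "Proportions and strata-adjusted difference in proportions will be pooled using" Rubin's method. For the test, "Results from the CMH analysis will be combined using the Wilson-Hilferty transformation as described in" a cited paper, "to produce a pooled CMH test p-value". This is the only p-value described for the primary test. SAP 9.1.4, 9.2.1 and 9.2.4 refer back to it.

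The visible text does not say which tail of the pooled statistic gives the p-value. Appendix C, which covers multiple imputation, is redacted in the public version.

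**The concern.** Wilson-Hilferty turns a chi-square into an approximately normal variable through its cube root. The approximation improves as the degrees of freedom rise, and 1 is the least favourable case. If the transformed statistic is not quite standard normal in the tail, comparing its p-value with 0.025 does not give a test of size 0.025. This p-value is the one that SAP 4.4 compares with alpha for both doses and for the key secondary hierarchy, so any departure carries through all the confirmatory tests. The departure is also avoidable: the signed square root of the same CMH statistic is already close to normal and can be pooled directly.

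**Working it through.** **Inputs.** From the documents: two-sided alpha 0.025 per dose (SAP 4.4); 84 per arm, 20% v 50% (SAP 4.2); 1:1:1 allocation (SAP 4.3). Assumed, because the documents give no missing-data rate: 0-20% missing, extended to 30% in one check.

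**The plan's own figure.** Power = Φ{[d√n − z√(2p̄q̄)] / √(p₁q₁ + p₂q₂)} with d = 0.30, n = 84, p̄ = 0.35 and z = 2.241. This is Φ{[2.750 − 1.512] / 0.640} = Φ(1.933) = 97.3%, so the stated 90% or more holds.

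**The transform at 1 df.** W = (X^(1/3) − 7/9) / √(2/9), referred to N(0,1).
- Upper tail: reject when X > (7/9 + 1.960 × 0.4714)³ = 1.7017³ = 4.928. The chi-square(1) probability above that is 0.0264. The exact cut-off for 0.025 is 5.024.
- Two-sided normal p-value: reject when X > (7/9 + 2.2414 × 0.4714)³ = 1.8344³ = 6.173, with true probability 0.0130. At X = 0, W is −0.7778/0.4714 = −1.65, so the lower tail can never reject.

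These are large-sample values with no between-imputation variance.

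**With multiple imputation.** Simulated size under the null: response rate 20%, 84 per arm, 14 equal strata, 50 imputations by arm, data missing completely at random, 20,000 trials, Monte Carlo standard error about 0.0011.

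| Missing | W-H, upper tail | W-H, two-sided | Signed CMH z | Rubin-pooled risk difference |
|---|---|---|---|---|
| 0% | 0.0267 | 0.0130 | 0.0253 | 0.0280 |
| 5% | 0.0248 | 0.0110 | 0.0238 | 0.0265 |
| 10% | 0.0271 | 0.0132 | 0.0256 | 0.0282 |
| 15% | 0.0270 | 0.0126 | 0.0257 | 0.0275 |
| 20% | 0.0267 | 0.0143 | 0.0255 | 0.0266 |
| 30% | 0.0293 | 0.0156 | 0.0272 | 0.0275 |

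A second, paired simulation (40,000 trials per setting, 0-20% missing) gave 0.0253-0.0277 for upper-tail Wilson-Hilferty and 0.0239-0.0256 for the signed z. Wilson-Hilferty rejected in every trial where the signed test rejected, and in a further 0.14-0.20% of trials. The excess is therefore systematic and not Monte Carlo noise.

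**Family-wise error.** With equal allocation and a shared placebo arm, the two test statistics have null correlation 0.5. Then 1 − P(|Z₁| < c, |Z₂| < c) is:
- 0.0465 at exactly 0.025 per dose
- 0.0490 at 0.0264 per dose
- 0.0245 at 0.0130 per dose

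**Power, 20% v 50%, no missing data.** By formula, 97.3% at exact 0.025, 97.5% at 0.0264 and 95.3% at 0.0130. With 15% missing, simulated power is 94.0% (upper tail), 93.8% (signed z) and 90.6% (two-sided reading).

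**The case against.** Four arguments can be made for leaving the plan alone.

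- **The excess is no worse than other approximations in the plan.** The test implied by the Rubin-pooled risk difference, which gives the 97.5% confidence interval, ran at 0.0265-0.0282 in the same simulation. This stands, and it keeps the point minor. It does not make the excess noise: the paired comparison shows it always goes one way.
- **Overall alpha is not breached.** A reader might double 0.0264 and infer a family-wise error of 0.053. That sum is only an upper bound. It ignores the shared placebo arm, which brings the figure to about 0.049. In one further simulation (true rate 30%, 10-20% missing) the per-dose size was 0.0272-0.0277, which would correspond to 0.0504-0.0513. The signed z itself ran at 0.0261 there, so part of that excess comes from imputation and not from the transform.
- **The conservative branch may never occur.** A reader might infer that the real size is 0.013 and that power is being lost. The documents do not support this: the visible SAP does not say that a two-sided normal p-value will be taken, and the cited paper or the redacted appendix may settle the tail. Even on that reading, power at the planned rates is 95.3%, above the stated 90%.
- **The loss of sign matters little.** Squaring removes the direction in each imputed data set, but the signed pooled difference and its interval are reported beside the p-value.

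**Conclusion.** The point holds as a small correction. Used as an upper-tail p-value, the planned pooling is slightly anti-conservative: 0.0264 per dose with no missing data, and about 0.025 to 0.028 over an assumed 0-20% missing, an excess of about 0.0014 to 0.002. The overall two-sided 0.05 is essentially kept, so this should not be read as a failure of the multiplicity scheme. If the pooled transform were instead given a two-sided normal p-value, the size would be about 0.013 and power at 20% v 50% would fall from 97.3% to 95.3%. That case is conditional on an implementation the visible text leaves open. The sizes with missing data rest on data missing completely at random, direct imputation of the binary response by arm and equal strata, none of which the SAP specifies. Severity: minor.

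**What to change.** In SAP 9.1.1, and by reference in 9.1.4 and 9.2.1, replace the Wilson-Hilferty step as follows. In each imputed data set compute z = Σ(a − E) / √ΣV, where a is the number of responders on the dose in a stratum and E and V are its CMH mean and variance. Pool z over the M imputations by Rubin's rules with within-imputation variance 1, so that the total variance is 1 + (1 + 1/M)B, where B is the between-imputation variance. Take the two-sided p-value and compare it with 0.025. Keep Wilson-Hilferty only as a check.

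With nothing missing, this is the planned CMH test. Its simulated size was 0.0238 to 0.0257 over 0-20% missing in the tabulated simulation. Protocol 19.3.1 names the CMH test but not the pooling rule, so the edit falls in the SAP.

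The cost is one sentence, a few lines of code, and about 0.6 to 0.9 points less power than the upper-tail Wilson-Hilferty version at 20% v 40-45% with 15% missing. Merely naming the upper tail would remove the ambiguity but leave the small excess.
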